5.1.4 Missing post-baseline efficacy data

The multiple imputation methodology assumes that the missing data is MAR, that is, the probability that an observation is missing may depend on the observed values but not the missing values. It also assumes that the parameters q of the data model and the parameters f of the missing data indicators are distinct. That is, knowing the values of q does not provide any additional information about f , and vice versa. If both MAR and the distinctness assumptions are satisfied, the missing data mechanism is said to be ignorable. The MI procedure provides three methods for imputing missing values and the method of choice depends on the type of missing data pattern. For monotone missing data patterns, either a parametric regression method that assumes multivariate normality or a nonparametric method that uses propensity scores is appropriate. For an arbitrary missing data pattern, a Markov chain Monte Carlo (MCMC) method that assumes multivariate normality can be used.

Assuming that the data are from a multivariate normal distribution, data augmentation is applied to Bayesian inference with missing data by repeating a series of imputation and posterior steps. These two steps are iterated long enough for the results to be reliable for a multiply imputed data set (Schafer 1997). The goal is to have the iterations converge to their stationary distribution and then to simulate an approximately independent draw of the missing values.

The number of iterations will be set to 25 (NIMPUTE = 25). Sample SAS code for MI using the MCMC method will be provided via instruction in the table shells.

Further, as an additional sensitivity analysis, the pattern-mixture model approach may be used to model the distribution of a response as the mixture of a distribution of the observed responses and a distribution of the missing responses, for which the missing values can be imputed under a plausible scenario for which the missing data are missing not at random. A tipping-point based pattern imputation will be applied in which systematically worse results than what's been imputed in the MAR MI analysis are imputed.

5.1.4.1 Multiple imputation sensitivity analysis steps

The following steps will be followed, in order to create the structure of the analysis dataset where missing values and appropriate variables could be imputed.

- Obtain participant ID (USUBJID), treatment group (TRT01PN), and stratification factor from ADSL (subject level analysis dataset)
- Obtain visit (AVISITN), parameter code (PARAMCD), parameter (PARAM), numeric score value (AVAL), character score value (AVALC), baseline value (BASE), change from baseline value (CHG), and derivation type (DTYPE) from the applicable efficacy dataset
- Transpose all data so the dataset takes the format of one observation per participant, and each visit becomes a variable within its own right, e.g. rows where AVISITN=2004, 2008, 2012 become the columns WK4, WK8, WK12, etc.
- Impute the missing data for MAR and MNAR separately according to the methods in next steps.

MAR multiple imputation steps:

Note that there will be a mix of categorical and continuous variables in the modelling of the missing data. Therefore, fully conditional specification (FCS) methods are employed within PROC MI to impute the missing data.

- FCS logistic is used for dichotomous variables; DISCRIM is used for categorical variables with more than 2 categories; REGPMM is used for continuous variables.
- WK0, WK4, WK8, WK12, WK16, WK20, WK24, WK28, WK32, WK36, WK40, WK44, W48, and W52 represent the AVAL variables for each of the visits respectively, where WK0 is baseline.
- Compute the average of values at WK48 and WK52 to create a virtual AVISITN for End of Follow-up Period 1 for the average for each subject and each imputation, and then add to the total dataset.

MNAR multiple imputations steps:

- Here is an implementation of the pattern-mixture model approach that uses a tipping-point-based pattern of imputation, assuming systematically worse results than what's been imputed in the MAR MI analysis.
- For this purpose, a delta-adjustment approach will be followed, whereby a systematic shift will be added to all imputed values of the total HFMSE (or RULM) score for the OAV101 treatment group, and no shift will be added to the sham administration arm, to estimate the treatment effect in a conservative scenario.
- The choice of these delta values will be based on clinical/practical judgement to reflect plausible difference that could have occurred.
- If a tipping-point, i.e. a shift that leads to a change in the analysis results such that a non-significant p-value is identified, clinical judgement will be further used to ascertain the likelihood of the relevant shift to have happened in practice. The larger the shift, the more robust the results from the primary analysis will be.
- This delta-adjustment will be applied for all data points that were imputed for the MAR MI analysis using the following procedure:
 - Select the shift value
 - All values imputed using the MAR MI analysis are 'adjusted' by adding a constant shift
 - The step above is repeated for all relevant shift values
- The following negative shifts for the total HFMSE (or RULM) score may be considered: -1, -2, -3, -4, and -5.
- For each of these shift values, an ANCOVA model will be used, by imputation, for analysis including treatment, strata and the baseline HFMSE total score or baseline RULM total score, as applicable, as covariate. Pooled estimates for the difference between OAV101 and sham in the LSM for change from baseline to End of Follow-up Period 1 in the total HFMSE (or RULM) score will be presented alongside p-values for each set of shift values.

MAR and MNAR modeling step:

- Given a complete data set with all values are available at each visit after imputation, a fixed-effect model can be used. For the change from baseline in HFMSE (or RULM) analysis, an ANCOVA model will be used including treatment, strata and the baseline HFMSE total score or baseline RULM total score, as applicable, as covariate. For the achievement of at least a 3-point improvement from baseline in HFMSE total score at the end of Follow-up Period 1, a logistic regression model will be used including treatment, strata and the baseline HFMSE total score as covariate.

MAR and MNAR combining step:

- The output dataset with the treatment LSMs (LSMEANS) and the treatment differences are then sorted, manipulated and read into PROC MIANALYZE to combine the individual sets of imputed results into one set of overall results. Additional details on SAS code will be provided in the table shells.

5.2 AEs coding/grading

Verbatim terms of AEs, including important identified and important potential risks, will be encoded by means of MedDRA according to the data management plan.

5.3 Laboratory parameters derivations

Hy's law criteria apply (see [Section 2.7.3](#)).

5.4 Statistical models

Not applicable.

5.4.1 Analysis supporting primary objective(s)

Not applicable.

5.4.2 Analysis supporting secondary objective(s)

Not applicable.

5.5 Rule of exclusion criteria of analysis sets

Analysis Set	Criteria that cause participants to be excluded
ITT	Screened but not randomized
FAS, SAF	Randomized but not treated during Treatment Period 1
ATP2	Not treated during Treatment Period 2

5.6 Clinically significant vital sign values

Vital sign results will be flagged as clinically significant if they meet the pre-specified criteria which are defined as follows.

Systolic and Diastolic Blood Pressure:

- For participants aged <18 years at the time of assessment, diastolic and systolic blood pressure values greater than or equal to the corresponding to the 90th percentile value for age, gender, and height will be used to classify 'high' clinically significant values. The relevant values are contained in Table 4 (BP Levels for Boys by Age and Height Percentile) and Table 5 (BP Levels for Girls by Age and Height Percentile) of Flynn 2017.
 - Participants aged ≥ 2 to <3 years at the time of assessment will utilize the blood pressure levels defined for age 2 years, participants aged ≥ 3 to <4 years at the time of assessment will utilize the blood pressure levels defined for age 3 years, etc.

- Height percentile will be defined using the height at the time of assessment, or the most recently recorded height prior to the assessment if the height at the time of assessment is not available. Participants with a height which falls between two percentiles will be classified according to the lower of the two percentiles. For example, if a girl participant aged 2 years at the time of assessment has a height of 90.0cm, they would fall between the 25th percentile for height (88.6cm) and the 50th percentile for height (91.1cm). In this case, the participant would be considered to belong in the 25th percentile for height and the 90th percentile for blood pressure according to that 25th percentile for height will be utilized for classification purposes.
- For participants aged 18 years and above at the time of assessment, systolic blood pressure values ≥ 120 mmHg and diastolic blood pressure values ≥ 80 mmHg will be classified as 'high' clinically significant values.
- For all participants regardless of age at assessment, systolic blood pressure values below the 5th percentile will be classified as 'low' clinically significant values. The 5th percentile value can be estimated using the following formula: 70 mmHg + (2*participant's age in years).

Temperature:

- For participants <18 years at the time of assessment, temperature values $\geq 38.4^{\circ}\text{C}$ will be classified as 'high' clinically significant.
- For participants ≥ 18 years at the time of assessment, temperature values $\geq 39.1^{\circ}\text{C}$ will be classified as 'high' clinically significant.
- For all participants regardless of age at assessment, temperature values $\leq 35^{\circ}\text{C}$ will be classified as 'low' clinically significant.

Pulse rate:

The criteria for classifying high and low pulse rate values are contained in the table below (Flemming 2011).

Age at assessment	High (bpm)	Low (bpm)
2 to <3 years	>128	<92
3 to <4 years	>123	<86
4 to <6 years	>117	<81
6 to <8 years	>111	<74
8 to <12 years	>103	<67
12 to <15 years	>96	<62
15 to <18 years	>92	<58
≥ 18 years	≥ 120 with increase from updated baseline ¹ of ≥ 15 bpm	≤ 50 with decrease from updated baseline ¹ of ≥ 15 bpm

¹Updated baseline is the last value collected before the participant's 18th birthday.

Weight

- For participants <18 years at the time of assessment, weight values which reflect an increase from baseline of ≥ 2 BMI-for-age percentile categories will be classified as 'high' clinically significant; weight values which reflect a decrease from baseline of ≥ 2 BMI-for-age percentile categories will be classified as 'low' clinically significant.
 - Baseline BMI-for-age weight status categories are underweight (less than the 5th percentile), healthy weight (5th percentile to less than the 85th percentile), overweight (85th to less than the 95th percentile) and obese (equal to or greater than the 95th percentile).
 - BMI-for-age percentile categories (P1 to P99) are obtained from the WHO Growth Charts (For ≥ 5 years: [\[https://www.who.int/tools/growth-reference-data-for-5to19-years/indicators/bmi-for-age\]](https://www.who.int/tools/growth-reference-data-for-5to19-years/indicators/bmi-for-age), For <5 years: [\[https://www.who.int/toolkits/child-growth-standards/standards/body-mass-index-for-age-bmi-for-age\]](https://www.who.int/toolkits/child-growth-standards/standards/body-mass-index-for-age-bmi-for-age) [\[https://www.who.int/toolkits/child-growth-standards/standards/body-mass-index-for-age-bmi-for-age\]](https://www.who.int/toolkits/child-growth-standards/standards/body-mass-index-for-age-bmi-for-age)).

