 - An active infectious process requiring systemic therapy intended to eliminate the infection within 30 days prior to dosing of OAV101 or the sham procedure
 - An active but untreated viral or bacterial infectious process within 30 days prior to dosing of OAV101 or the sham procedure
 - Febrile illness within 30 days prior to OAV101 administration or sham procedure
8. Administration of vaccines within 2 weeks prior to injection of OAV101 or sham procedure.
9. Clinical or radiological signs of aspiration within 30 days prior to Day 1.
10. Requiring invasive ventilation, awake noninvasive ventilation for > 6 hours during a 24-hour period, noninvasive ventilation for > 12 hours during a 24-hour period or requiring tracheostomy within 30 days prior to Day 1.

11. Awake hypoxemia (defined as O₂ saturation < 95% in room air) within 30 days prior to Day 1.
NOTE: For altitudes > 1000 m, awake hypoxemia is defined as O₂ saturation < 92% in room air
NOTE: For altitudes > 2500 m, awake hypoxemia is defined as O₂ saturation < 90% in room air
12. Hepatic dysfunction (i.e., ALT, TBL, GGT or GLDH, > ULN (i.e., CTCAE grade 1 or greater)) at Screening Visit 1.
NOTE: In the absence of other liver laboratory abnormalities, isolated AST elevation is not considered exclusionary
13. Complications at screening that would interfere with motor efficacy assessments including but not limited to:
 - Presence of severe contractures (e.g., hip flexion contracture) which limits the participant's ability to be positioned in prone for HFMSE item administration
 - Scoliosis with a Cobb angle > 40 degrees in a sitting position, evident on x-ray examination at Screening
14. BMI < 3rd percentile if considered clinically significant by the investigator
NOTE: BMI is based on the WHO Child Growth Standards ([WHO 2022a](#)) and WHO Growth reference data for 5-19 years ([WHO 2022b](#)).
15. History of untreated or uncorrected vitamin deficiencies which can produce sensory neuropathies such as pyridoxine deficiency (B6).
16. Concomitant use of any of the following medication categories within 90 days prior to study treatment (Day 1):
 - Ongoing systemic immunosuppressive therapy (e.g., corticosteroids (except for prophylactic use for OAV101 dosing), cyclosporine, tacrolimus, methotrexate, cyclophosphamide, intravenous immunoglobulin, rituximab), plasmapheresis, immunomodulators (e.g., adalimumab)
17. Inability to tolerate corticosteroids administered by mouth or gastrostomy tube.

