8.4.4 Vital signs

Vital sign parameters include blood pressure, respiratory rate, pulse, temperature, and pulse oximetry.

Vital signs will be obtained as specified in the [Table 8-1](#). On Day 1 and Week 52+1 Day (OAV101 administration or sham procedure), vital signs, with the exception of blood pressure, will be recorded pre-dose and then monitored every 15 (\pm 5) minutes for the first 1 hour, every 30 (\pm 10) minutes until 2 hours, every 2 hours (\pm 15 minutes) until 8 hours, and every 4 hours (\pm 30 minutes) until 16 hours. Blood pressure will be recorded pre-dose and every 8 hours (\pm 2 hours) through 16 hours.

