2.7.4.2 Vital signs

Vital signs will be assessed at the scheduled visits in accordance with the Schedule of Study Assessments. All summaries of data will be based on the SAF.

Observed values as well as change from baseline values will be summarized at each scheduled visit through the end of Follow-up Period 1 using descriptive statistics for systolic blood pressure, diastolic blood pressure, respiratory rate, temperature, pulse, and pulse oximetry.

Vital sign results will be flagged as clinically significant if they meet the pre-specified criteria which are defined in Appendix 5.6. The number and percentage of patients meeting each clinically significant criterion through the end of Follow-up Period 1 will be summarized. A second output will be produced to detail post-baseline, post-OAV101 treatment values meeting each clinically significant criterion. In this second summary, only vital sign values reported on/after OAV101 dosing (during Treatment Period 1 and through the end of study for participants originally randomized to OAV101, during Treatment Period 2 and through the end of study for participants originally randomized to sham administration) will be considered. A listing of all clinically significant vital sign values will also be produced.

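### Pulse oximetry is the only protocol vital sign with no reporting criterion in SAP 5.6, so a low saturation value cannot reach the flag table, the post-OAV101 output or the listing

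*SAP*

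**What the plan says.** Protocol 8.4.4 defines the set: "Vital sign parameters include blood pressure, respiratory rate, pulse, temperature, and pulse oximetry". On both procedure days, "vital signs, with the exception of blood pressure, will be recorded pre-dose and then monitored every 15" minutes for the first hour, then at widening intervals to 16 hours. Pulse oximetry therefore follows the dense schedule.

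SAP 2.7.4.2 has two layers. The first is a by-visit summary of observed values and changes from baseline, "using descriptive statistics for systolic blood pressure, diastolic blood pressure, respiratory rate, temperature, pulse, and pulse oximetry". The second is a set of threshold outputs: "Vital sign results will be flagged as clinically significant if they meet the pre-specified criteria which are defined in Appendix 5.6". From those flags come a count and percentage of patients per criterion through Follow-up Period 1, a second output restricted to values after OAV101, and a listing: "A listing of all clinically significant vital sign values will also be produced". The section plans no listing of unflagged vital signs.

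SAP 5.6 begins "Vital sign results will be flagged as clinically significant if they meet the pre-specified criteria which are defined as follows" and supplies the criteria for systolic and diastolic blood pressure, temperature, pulse rate, weight and respiratory rate. Pulse oximetry does not appear, and there is no redaction mark where a limit could have stood. Protocol Appendix 1 (16.1) gives no limit either and leaves the methods to the SAP.

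Numeric saturation limits do exist in the protocol, but only for eligibility. Exclusion criterion 11 in Section 5.2 reads "Awake hypoxemia (defined as O₂ saturation < 95% in room air) within 30 days prior to Day 1", with lower limits at altitude (92% above 1000 m, 90% above 2500 m). Section 3 repeats them for Period 2 and adds that the hypoxemia must be clinically significant in the investigator's judgement.

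**The concern.** Participants are children with neuromuscular weakness, and the entry criteria allow some use of non-invasive ventilation. OAV101 recipients are sedated or anesthetized and tilted head-down for 15 minutes after the injection (protocol 6.3). A fall in oxygen saturation is a natural thing to look for in that setting, and the protocol schedules repeated readings that would show it. The SAP then reports threshold counts by arm for every other vital sign, and for weight, but not for this one, and gives no reason. A programmer who follows SAP 5.6 as written would produce no oximetry row, and a reader of the flag table could take its absence to mean that nothing was found.

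**Working it through.** The plan states no figure here to reproduce. The check sets the lists side by side and then follows a low reading through the planned outputs.

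**1. Coverage**

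| Vital sign (protocol 8.4.4) | By-visit summary (SAP 2.7.4.2) | Limit in SAP 5.6 |
|---|---|---|
| Blood pressure | yes | high for systolic and diastolic; low for systolic only |
| Respiratory rate | yes | high and low |
| Pulse | yes | high and low |
| Temperature | yes | high and low |
| Pulse oximetry | yes | none |

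Four of five have a limit and one of five has none. With systolic and diastolic counted separately, it is five of six and one of six. Diastolic pressure is only partly covered, so pulse oximetry is the only sign with no limit at all. Weight, which the protocol places under anthropometry (8.4.6), does have one.

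**2. Readings affected.** From the 8.4.4 schedule for signs other than blood pressure:

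- every 15 minutes to 1 hour: 4
- every 30 minutes to 2 hours: 2
- every 2 hours to 8 hours: 3
- every 4 hours to 16 hours: 2

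Post-dose total: 4 + 2 + 3 + 2 = 11. The pre-dose reading makes 12. With 125 participants, Day 1 alone has 125 × 11 = 1,375 planned post-dose readings, none of which can be flagged at any value. The same schedule applies at Week 52 + 1 Day.

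**3. What the by-visit summary retains.** SAP 2.1 gives mean, standard deviation, median, minimum and maximum. In SAP 2.1.2 the Day 1 window for vital signs starts and ends on Day 1. Where several scheduled observations share a window, the one closest to the nominal time is used, and ties go to the latest. Windows are counted in days, so on a literal reading all Day 1 readings tie and the last is kept. An early fall that had recovered would then be missing even from the minimum. Protocol 12.5.2 speaks of summaries by visit and time, which would avoid this. The SAP does not repeat it and states in Section 1 that it supersedes the protocol's statistical considerations. The outcome depends on programming.

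**4. What the summary cannot show even if every reading is used.** As an illustration (the size and frequency are assumptions, not figures from the documents), let k of 75 OAV101 children fall 8 points and the rest not change. The shift in the mean is 8k/75:

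- k = 1: 8/75 = 0.11 points
- k = 4: 32/75 = 0.43 points
- k = 8: 64/75 = 0.85 points

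The minimum change is −8 in all three. Mean and minimum show that a fall occurred, but not directly in how many children. The count per arm is what a flag table gives.

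**5. The adverse event route.** Under protocol 10.1.1 an abnormal result is an adverse event only if it produces signs or symptoms, is judged clinically significant, or requires therapy. If reported, it enters the SAP 2.7.1 tables, including the table of events within 72 hours of treatment. Protocol 6.5 allows unblinded site staff to assess adverse events during the inpatient days, so for that window the judgement may be unblinded.

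**The case against.** The strongest reply is that little is lost. The secondary safety endpoint is change from baseline in vital signs, and SAP 2.7.4.2 delivers that for pulse oximetry with a minimum and a maximum. The protocol nowhere requires a threshold for every vital sign. Children stay in a monitored setting for 24 to 48 hours, clinically important events must be recorded, and the 72-hour table compares the arms over the period of interest. Most of this stands: no protocol requirement is breached, and the raw readings are collected.

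A reader might infer that a child who desaturates disappears from the safety outputs. The documents do not support that. The same child may be flagged on pulse or respiratory rate, may set the by-visit minimum, and may have a reported adverse event. What cannot be flagged is the saturation value itself.

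A reader might also infer that the protocol's 95%, 92% and 90% limits already define clinical significance for this trial. They do not. They are eligibility limits for awake children in room air, and for Period 2 the protocol adds investigator judgement to them. Applied to sedated or sleeping children, or to those on oxygen, they would flag readings outside their own definition.

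The reply does not explain why pulse oximetry alone has no criterion. Nor does it settle which Day 1 readings the by-visit summary will use.

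**Conclusion.** The point holds as a gap in planned safety reporting: one of five protocol vital signs has no criterion, so low values of it cannot enter either threshold output or the listing. Primary and secondary efficacy inference, alpha and the estimands are unaffected. It is a cheap improvement, not a threat to the trial's conclusions.

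The conclusion assumes that SAP 5.6 is complete as published, which the absence of a redaction mark supports, and that no redacted output elsewhere supplies a saturation threshold. Some respiratory material in the SAP is blacked out, but SAP 2.7.4.2 draws its flags from 5.6 alone. The possible loss of early Day 1 readings rests on a literal reading of the SAP 2.1.2 selection rule. No rate of desaturation is given in the documents, so the likely number of children affected cannot be stated.

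**What to change.** Reconcile SAP 5.6 and 2.7.4.2 with protocol 8.4.4:

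- Add a low pulse-oximetry flag to SAP 5.6, stated to be for reporting only and not for clinical management: a post-baseline value below a pre-specified limit in a participant whose last pre-dose value was not below it. This follows the logic of the new-QTcF categories in SAP 2.7.4.1. For participants given sham first, state which administration the pre-dose value refers to in the post-OAV101 output.
- Fix the limit in advance. The protocol's altitude-specific awake-hypoxemia limits are an available reference; if used, label them as awake, room-air limits.
- Include the flag in both SAP 2.7.4.2 outputs and in the listing.
- List each participant's lowest procedure-day value, and show procedure-day readings separately from later visits.
- If the sponsor prefers no limit, say so in SAP 5.6 and list all pulse-oximetry values.

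The cost is one criterion, one extra row in existing tables and a short listing, with no new saturation measurements. The downside is that sedation, sleep, supplemental oxygen and altitude may not be recorded with each reading, so procedure-day flags will need context before they are interpreted.

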Further details of the OAV101-related CCI can be found in the Investigator's Brochure.

Intravenous and intrathecal OAV101 administration: **CCI**

[REDACTED]

[REDACTED]

[REDACTED]

Thrombotic microangiopathy (TMA)

Intravenous administration overview: Thrombotic microangiopathy (TMA) is characterized by arteriole and capillary endothelial pathology and microvascular thrombosis. TMA presents clinically as a syndrome of thrombocytopenia, hemolytic anemia, and acute kidney injury. **CCI**

[REDACTED]

[REDACTED]

[REDACTED]

Intrathecal administration overview: **CCI**

[REDACTED]

Theoretical risk of tumorigenicity due to vector integration

There is a theoretical risk of tumorigenicity due to integration of AAV vector DNA into the genome. OAV101 (onasemnogene abeparvovec) is composed of a non-replicating AAV9 vector whose DNA persists largely in episomal form. Rare instances of random vector integration into human DNA are possible with recombinant AAV. The clinical relevance of individual integration events is unknown, but it is acknowledged that individual integration events could potentially contribute to a risk of tumorigenicity.

Risk of immunosuppression

All patients in the study will receive prophylaxis immunosuppression with prednisolone to mitigate safety risks associated with inflammation. The chronic use of corticosteroids may be associated with hypothalamic-pituitary-adrenal axis suppression, Cushing's syndrome and hyperglycemia which can be mitigated with adequate tapering. Increased susceptibility to new infections or exacerbation and dissemination of latent infections, as well as elevated blood pressure, salt and water retention, hypokalemia, and gastrointestinal perforation have been reported. Risks will be mitigated by close monitoring, and implementation of standard prophylaxis and tapering protocol ([Table 6-2](#)).

Risk of viral shedding

OAV101 DNA can be found in the blood, urine, saliva, and stool for up to a few weeks following injection. The risks associated with the shed vector are not known at this time; however, because the vector is non-pathogenic and cannot replicate, it is believed that the shed vector is unlikely to result in clinically significant adverse effect.

Risk of phlebotomy

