2.1.2 Analysis visit windows

Unless otherwise specified, **analysis visit windows** for efficacy and safety assessments which are summarized on a by-visit basis are defined based on study day post dosing. For by-visit endpoints, the time windows describe how data will be assigned to protocol-specified time points during follow up.

Period 2 windows defined below will be used for analyses of “on or after OAV101 administration” (i.e., OAS).

The analysis windows for respective assessments are as follows:

Vital Signs and Neurological Examination:

Period 1 windows:

Visit	Nominal day	Start day	End day
Day 1	Day 1	Day 1	Day 1
Day 2	Day 2	Day 2	Day 2
Day 3	Day 3	Day 3	Day 3
Week 1	Day 8	Day 4	Day 11
Week 2	Day 15	Day 12	Day 18
Week 3	Day 22	Day 19	Day 25
Week 4	Day 29	Day 26	Day 36
Week 6	Day 43	Day 37	Day 50
Week 8	Day 57	Day 51	Day 64

Visit	Nominal day	Start day	End day
Week 10	Day 71	Day 65	Day 78
Week 12	Day 85	Day 79	Day 99
Week 16	Day 113	Day 100	Day 127
Week 20	Day 141	Day 128	Day 155
Week 24	Day 169	Day 156	Day 183
Week 28	Day 197	Day 184	Day 211
Week 32	Day 225	Day 212	Day 239
Week 36	Day 253	Day 240	Day 267
Week 40	Day 281	Day 268	Day 295
Week 44	Day 309	Day 296	Day 323
Week 48	Day 337	Day 324	Day 351
Week 52	Day 365	Day 352	Week 52 + Day 1 – 1

Period 2 windows:

Visit (OAV-SHAM)	Visit (SHAM-OAV)	Nominal day	Start day	End day
Week 52 + Day 1	Day 1	Day 1	Day 1	Day 1
Week 52 + Day 2	Day 2	Day 2	Day 2	Day 2
Week 52 + Day 3	Day 3	Day 3	Day 3	Day 3
Week 53	Week 1	Day 8	Day 4	Day 11
Week 54	Week 2	Day 15	Day 12	Day 18
Week 55	Week 3	Day 22	Day 19	Day 25
Week 56	Week 4	Day 29	Day 26	Day 36
Week 58	Week 6	Day 43	Day 37	Day 50
Week 60	Week 8	Day 57	Day 51	Day 64
Week 62	Week 10	Day 71	Day 65	Day 78
Week 64	Week 12	Day 85	Day 79	Last participation day

Body Weight:

Period 1 windows:

Visit	Nominal day	Start day	End day
Day 1	Day 1	Day 1	Day 1
Day 2	Day 2	Day 2	Day 2
Week 1	Day 8	Day 3	Day 18

Visit	Nominal day	Start day	End day
Week 4	Day 29	Day 19	Day 43
Week 8	Day 57	Day 44	Day 71
Week 12	Day 85	Day 72	Day 99
Week 16	Day 113	Day 100	Day 127
Week 20	Day 141	Day 128	Day 155
Week 24	Day 169	Day 156	Day 183
Week 28	Day 197	Day 184	Day 211
Week 32	Day 225	Day 212	Day 239
Week 36	Day 253	Day 240	Day 267
Week 40	Day 281	Day 268	Day 295
Week 44	Day 309	Day 296	Day 323
Week 48	Day 337	Day 324	Day 351
Week 52	Day 365	Day 352	Week 52 + Day 1 – 1

Period 2 windows:

Visit (OAV- SHAM)	Visit (SHAM- OAV)	Nominal day	Start day	End day

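### The 'high' blood pressure count rests on any single reading at or above the 90th percentile over a year of visits; add a count limited to the prednisolone/placebo course

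*SAP*

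**What the plan says.** SAP 5.6 sets the 'high' limit for participants under 18: "diastolic and systolic blood pressure values greater than or equal to the corresponding to the 90th percentile value for age, gender, and height". SAP 2.7.4.2 applies it to individual results ("Vital sign results will be flagged as clinically significant if they meet the pre-specified criteria") and then counts people: "The number and percentage of patients meeting each clinically significant criterion through the end of Follow-up Period 1 will be summarized". Neither section asks for a repeat reading, persistence, or a baseline value below the limit.

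The windows headed "Vital Signs and Neurological Examination" in SAP 2.1.2 give 21 Period 1 occasions: Days 1, 2 and 3, Weeks 1, 2, 3, 4, 6, 8, 10 and 12, then every four weeks to Week 52. Day 3 is optional. On the dosing day there are further readings (Protocol 8.4.4: "Blood pressure will be recorded pre-dose and every 8 hours", through 16 hours).

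Protocol 4.5.3 lists effects reported with corticosteroids, "as well as elevated blood pressure, salt and water retention" among them. Under Protocol 6.2, the OAV101 arm receives prednisolone and the sham arm matching placebo. The course length is redacted.

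**The concern.** By construction, about 10% of reference-population readings lie at or above the 90th percentile on any one occasion. A count that needs only one such reading in about 20 visits partly measures how often pressure was taken. Both arms carry that background for the whole year, whereas a steroid effect would act in one arm and for part of the year. The arm ratio in this table is therefore pulled towards 1.

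What is at stake is the readability of one descriptive safety table on a risk that the protocol names. No efficacy result depends on it.

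**Working it through.** The documents give no expected flag rate, so there is no plan figure to reproduce.

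**Inputs from the documents.** Limit at the 90th percentile (SAP 5.6), so c = 1.2816 on the standard normal scale. Visits k = 19: Day 2 plus the 18 week visits (SAP 2.1.2). Eight of these fall in Weeks 1-12. Arm sizes 75 and 50 (SAP 3).

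**Assumptions.** Readings follow the reference distribution, with equal within-child correlation ρ between visits, varied from 0.3 to 0.9. Prednisolone raises systolic pressure by δ = 0.5 SD at the eight Week 1-12 visits, in the OAV101 arm only.

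**Step 1: background.** With independent readings, 1 − 0.9^19 = 86% would be flagged at least once. With correlation ρ,

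P(ever flagged) = 1 − ∫ φ(u) [Φ((c − √ρ·u)/√(1−ρ))]^k du.

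For systolic pressure this gives 64%, 51%, 38%, 31% and 23% at ρ = 0.3, 0.5, 0.7, 0.8 and 0.9. The number of visits matters little: at ρ = 0.5, k = 18 gives 50% and k = 23 gives 54%.

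**Step 2: planned count against a count in Weeks 1-12.** In the OAV101 arm, c is replaced by c − δ for the eight shifted visits. The count in Weeks 1-12 uses only those eight visits, still on a single reading. Nominal power is Φ((d − 1.96·SE0)/SE1), where d is the difference in proportions, SE0 its pooled and SE1 its unpooled standard error.

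| ρ | Planned count: OAV101 v sham | Ratio | Power | Weeks 1-12: OAV101 v sham | Ratio | Power |
|---|---|---|---|---|---|---|
| 0.3 | 77.5% v 63.9% | 1.21 | 0.38 | 70.4% v 44.4% | 1.59 | 0.83 |
| 0.5 | 65.0% v 50.8% | 1.28 | 0.35 | 60.4% v 36.7% | 1.65 | 0.75 |
| 0.7 | 51.9% v 37.9% | 1.37 | 0.33 | 49.8% v 28.8% | 1.73 | 0.65 |
| 0.8 | 44.8% v 31.0% | 1.44 | 0.33 | 43.8% v 24.5% | 1.79 | 0.60 |
| 0.9 | 36.8% v 23.4% | 1.57 | 0.35 | 36.6% v 19.5% | 1.87 | 0.54 |

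Worked cell (ρ = 0.3, Weeks 1-12): d = 0.704 − 0.444 = 0.260. The pooled proportion is (75 × 0.704 + 50 × 0.444)/125 = 0.600. SE0 = √(0.600 × 0.400 × (1/75 + 1/50)) = 0.0894. SE1 = √(0.704 × 0.296/75 + 0.444 × 0.556/50) = 0.0878. Power = Φ((0.260 − 0.1753)/0.0878) = 0.83.

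**Step 3: would a two-consecutive-visit rule help?** This was simulated under the same model. Over the whole period its power is 0.29 to 0.40, much the same as the planned count. Within Weeks 1-12 it is 0.45 to 0.68, below the single-reading count at every ρ. The gain comes from the time window; the repeat requirement takes some of it away.

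**Step 4: the summary that is already planned.** For mean change from one baseline reading to one visit, in SD units, SE = √(2(1−ρ)) × √(1/75 + 1/50). At ρ = 0.5 this is 0.183, so power = Φ(0.5/0.183 − 1.96) = 0.78. At ρ = 0.3 and 0.7 it is 0.64 and 0.94.

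**The case against.** The strongest reply is that this table is not the only place where a steroid effect would appear. SAP 2.7.4.2 also summarises systolic and diastolic values and change from baseline at every scheduled visit. SAP 2.7.1 gives a separate summary of adverse events related to prednisolone/placebo. All flagged values are listed. Step 4 shows that the by-visit change is the more sensitive output under the same assumed shift. This stands: the effect is diluted in one descriptive table, but it is not lost from the report. No test is planned on the table, so the power figures only illustrate.

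A reader might infer that most sham children would be labelled with high blood pressure. The documents do not support that. They give no within-child correlation, and for systolic pressure alone the background falls below half by ρ = 0.7. Higher figures come from merging systolic and diastolic flags, whereas the SAP counts each criterion. The percentiles also describe a reference population, not non-ambulatory children with SMA.

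A reader might also see the blood pressure rule as an exception within the SAP. The evidence is mixed. The QTcF flag must be new relative to baseline (SAP 2.7.4.1), and the pulse rule at 18 and over has the condition "with increase from updated baseline". But the under-18 pulse and respiratory-rate flags, and the blood pressure flag at 18 and over, are single-reading rules too.

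On height, the SAP says "Participants with a height which falls between two percentiles will be classified according to the lower of the two percentiles". This would lower the limit only if the limit rises with height. The limits sit in an outside table, so no weight is placed on it.

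**Conclusion.** The point holds as a limited one. The 'high' count can be met by one reading at the 90th percentile over about 20 visits. Under assumed correlations of 0.3 to 0.9, roughly a quarter to two thirds of reference-population children would be flagged on systolic pressure alone. The whole-period table is therefore a weak display of a prednisolone effect: the difference between arms is 13 to 14 percentage points under the assumed shift, against 17 to 26 points when the same flag is counted within Weeks 1-12.

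These sizes rest on the correlation, the 0.5 SD shift and the 12-week window, none of which the documents supply. The absolute rates may not carry over to this population. The direction does not depend on the exact correlation: the count in Weeks 1-12 had the larger difference, ratio and power at every value tried. A conclusion that the trial would miss a blood pressure effect, or that the flag must be replaced, goes beyond the documents.

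**What to change.** In SAP 2.7.4.2, keep the 90th-percentile flag and the whole-period count. Add the number and percentage of participants flagged 'high', by arm, separately for the prednisolone/placebo course and for the rest of Follow-up Period 1. Define the course by the same planned visit windows in both arms, so that longer individual courses do not give one arm more readings.

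Do not replace the count with a two-consecutive-visit rule. It lowers power within the window and removes children with a single high reading from the table. At most, show it as an extra row.

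The cost is a sentence in the SAP and one more descriptive safety table. No data collection changes, and no flagged child drops out of the existing count.
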